3.5.7 Echocardiogram

The analysis will be performed based on the safety analysis set.

Echocardiographic findings will be summarized.

All abnormal and clinically significant echocardiographic findings will be tabulated.

3.5.8 ECOG Score

The analysis will be performed based on the safety analysis set.

Crosstabs summarizing the highest post-baseline ECOG scores relative to baseline scores will be summarized.

3.5.9 Vital Signs

The analysis will be performed based on the safety analysis set.

Vital signs at each visit from baseline and their changes from baseline will be statistically described.

3.6 EFFICACY ANALYSIS

The analysis will be performed based on the safety analysis set.

The investigator will perform efficacy assessments according to the Response Evaluation Criteria in Solid Tumors Version 1.1 (RECIST v1.1).

Objective Response (ORR): The number and proportion of subjects who achieve objective tumor response (CR or PR) will be summarized. Objective response rate will be determined along with 95% confidence interval. (Clopper-Pearson method).

Progression Free Survival (PFS): PFS is defined as the time from the date of first study dose to disease progression or death (whichever occurs first). Subjects without event (no disease progression or death) will be censored at the date of “last tumor assessment”. Kaplan-Meier methodology will be used to estimate median PFS, PFS rate at various time points, and their 95% confidence intervals. Kaplan-Meier curves will be constructed to provide a visual description of the PFS change with time.

Duration of response (DOR): Duration of response (complete response or partial response) for responders is defined as the time interval between the date of the earliest qualifying response and the date of PD or death for any cause (whichever occurs earlier). For subjects who do not have progressive disease following the qualifying response, duration of response will be censored on the date of last evaluable tumor assessment. Subjects without tumor assessment records after the earliest date of qualifying response will be censored on the earliest date of qualifying response. The analysis method is the same as that of PFS.

Time to Progression (TTP): TTP is defined as the time from the date of first study dose to disease progression. Subjects without event (no disease progression) will be censored at the date of “last tumor assessment”. The analysis method is the same as that of PFS.

Disease Control Rate: Disease control rate (DCR) is defined as the proportion of subjects who achieve CR, PR, and SD based on RECIST v1.1. The disease control rate and its 95% confidence interval (Clopper-Pearson method) will be calculated.

Overall Survival (OS): Overall survival is defined as the time interval between the date of the first investigational product dose to the date of death from any cause. Subjects who are still alive at the analysis cutoff date will be censored at the date of the last known survival. The analysis method is the same as that of PFS.

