## 10.4. EFFICACY ANALYSIS

Response based on investigators' assessment will be collected while on study every 9 weeks within 1 year, and every 12 weeks thereafter according to RECIST v1.1.

CSTONE Confidential Page 105 of 139

- **Objective Response:** The number and proportion of subjects who achieve objective tumor response (CR or PR) will be summarized. Objective response rate will be determined along with 95% confidence interval.
- **Progression Free Survival (PFS):** PFS is defined as the time from the date of first study dose to disease progression or death (whichever occurs first). Subjects without event (no disease progression or death) will be censored at the date of "last tumor assessment". Kaplan-Meier methodology will be used to estimate median PFS, PFS rate at various time points, and their 95% confidence intervals. Kaplan-Meier curves will be constructed to provide a visual description of the PFS change with time.
- **Duration of Response:** Duration of response for responders (CR or PR) is defined as the time interval between the date of the earliest qualifying response and the date of PD or death for any cause (whichever occurs earlier). For subjects who are alive without progression following the qualifying response, duration of response will be censored on the date of last evaluable tumor assessment or last follow-up for progression of disease.
- **Time to Progression (TTP): TTP is defined as the time from the date of first study dose to disease progression. Subjects without event (no disease progression) will be censored at the date of "last tumor assessment". Kaplan-Meier methodology will be used to estimate median TTP and 95% confidence interval.**
- **Disease Control Rate:** Disease control rate (DCR) is defined as the proportion of subjects who achieve CR, PR, and SD based on RECIST v1.1.
- **Overall Survival:** Overall survival is defined as the time interval between the date of the first investigational product dose to the date of death from any cause.

Kaplan-Meier methodology will be used to estimate median OS, OS rate at various time points, and their 95% confidence intervals.

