#### Evaluation of Best Overall Response

The best overall response is the best response recorded from the start of the investigational product treatment until the end of treatment taking into account any requirement for confirmation. On occasion that a response may not be documented until after the end of therapy, so protocols should be clear if post-treatment assessments are to be considered in determination of best overall response. Protocols must specify how any new therapy introduced before progression will affect best response designation. The subject's best overall response assignment will depend on the findings

CSTONE Confidential Page 122 of 139 of both target and non-target disease and will also take into consideration the appearance of new lesions. Furthermore, depending on the nature of the trial and the protocol requirements, it may also require confirmatory measurement. Specifically, in non-randomized trials where response is the primary endpoint, confirmation of PR or CR is needed to deem either one the "best overall response".

The best overall response is determined once all the data for the subject is known. Best response determination in trials where confirmation of complete or partial response IS NOT required: Best response in these trials is defined as the best response across all time points (for example, a subject who has SD at first assessment, PR at second assessment, and PD on last assessment has a best overall response of PR). When SD is believed to be best response, it must also meet the protocol specified minimum time from baseline. If the minimum time is not met when SD is otherwise the best time point response, the subject's best response depends on the subsequent assessments. For example, a subject who has SD at first assessment, PD at second and does not meet minimum duration for SD, will have a best response of PD. The same subject lost to follow-up after the first SD assessment would be considered unevaluable.

Target Lesions	Non-target Lesions	New Lesions	Overall Response
CR	CR	No	CR
CR	Non-CR/non-	No	PR
CR	PD Not	No	PR
PR	evaluated Non-	No	PR
	PD or not all		
	evaluated		
SD	Non-PD or not	No	SD
	all evaluated		
Not all evaluated	Non-PD	No	NE
PD	Any	Yes or No	PD
Any	PD	Yes or No	PD
Any	Any	Yes	PD

CR = complete response; PR = partial response; SD = stable disease; and PD = progressive disease.

Note:

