When nodal disease is included in the sum of target lesions and the nodes decrease to "normal" size (<10 mm), they may still have a measurement reported on scans. This measurement should be recorded even though the nodes are normal in order not to overstate progression should it be based on increase in size of the nodes. As noted earlier, this means that subjects with CR may not have a total sum of "zero" on the eCRF.

In trials where confirmation of response is required, repeated 'NE' time point assessments may complicate best response determination. The analysis plan for the trial must address how missing data/assessments will be addressed in determination of response and progression. For example, in most trials it is reasonable to consider a subject with time point responses of PR-NE-PR as a confirmed response.

Subjects with a global deterioration of health status requiring discontinuation of treatment

without objective evidence of disease progression at that time should be reported as "symptomatic deterioration". Every effort should be made to document objective progression even after discontinuation of treatment. Symptomatic deterioration is not a descriptor of an objective response: it is a reason for stopping trial therapy.

Conditions that define "early progression, early death, and in-evaluability" are trial specific and should be clearly described in each protocol (depending on treatment duration, treatment periodicity).

In some circumstances it may be difficult to distinguish residual disease from normal tissue. When the evaluation of complete response depends upon this determination, it is recommended that the residual lesion be investigated (fine needle aspirate/biopsy) before assigning a status of complete response. FDG-PET may be used to upgrade a response to a CR in a manner similar to a biopsy in cases where a residual radiographic abnormality is thought to represent fibrosis or scarring. The use of FDG-PET in this circumstance should be prospectively described in the protocol and supported by disease specific medical literature for the indication. However, it must be acknowledged that both approaches may lead to false positive CR due to limitations of FDG-PET and biopsy resolution/ sensitivity.

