# CONFIRMATORY MEASUREMENT/DURATION OF RESPONSE

#### Confirmation

In non-randomized trials where response is the primary endpoint, confirmation of PR and CR is required to ensure that the responses identified are not the result of measurement error. This will also permit appropriate interpretation of results in the context of historical data where response has traditionally required confirmation in such trials. However, in all other circumstances, i.e., in randomized clinical trials (phase II or III) or trials where stable disease or progression are the primary endpoints, confirmation of response is not required since it will not add value to the interpretation of trial results. However, elimination of the requirement for response confirmation may increase the importance of review by the sites to protect against bias, in particular in trials which are not blinded.

In the case of SD, measurements must have met the SD criteria at least once after trial entry at a minimum interval (in general not less than 6 weeks).

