#### Duration of Overall Response

The duration of overall response is measured from the time measurement criteria are first met for CR/PR (whichever is first recorded) until the first date that recurrent or progressive disease is objectively documented (taking as reference for progressive disease the smallest measurements recorded on study).

The duration of overall complete response is measured from the time measurement criteria are first met for CR until the first date that recurrent disease is objectively documented.

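### Does the Phase II response rate leave open whether only confirmed responses count?

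*SAP*

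**What the plan says.** SAP 2.4.1 makes ORR based on RECIST v1.1 the Phase II primary endpoint. SAP 3.6 describes the analysis: "Objective Response (ORR): The number and proportion of subjects who achieve objective tumor response (CR or PR) will be summarized", with a Clopper-Pearson 95% interval. Protocol 10.4 uses the same sentence. SAP 2.2 and protocol 10.1 set non-binding go/no-go criteria on the number of responses, read once every subject has at least two post-baseline assessments.

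The confirmation rule is in protocol Appendix 2, under Confirmation: "In non-randomized trials where response is the primary endpoint, confirmation of PR and CR is required". The section on best overall response says the same. Footnote k to Tables 2 and 3 in protocol 1.2 (copied in SAP Appendix 2) names Appendix 2 as the assessment standard and requires a confirmatory assessment four weeks after a CR or PR, in Phase Ib and in Phase II.

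On missing assessments, Appendix 2 says: "The analysis plan for the trial must address how missing data/assessments will be addressed in determination of response and progression". SAP 3.9 says only that missing values are not imputed, and refers for efficacy to Section 3.5, which is the safety section. For duration of response, SAP 3.6 adds: "Subjects without tumor assessment records after the earliest date of qualifying response will be censored on the earliest date of qualifying response".

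**The concern.** The sections an analyst programs from never mention confirmation. Appendix 2 requires it, the schedule pays for the scan, and no analysis text says how that scan is used. Several details add to the doubt. Inside the SAP, the pointer to Appendix 2 lands on the schedule of activities. The term qualifying response is not defined. The duration rule quoted above describes a responder with no later scan, which looks like an unconfirmed responder. Appendix 2 asks the analysis plan for a rule on missing assessments, and the SAP has none specific to response. The go/no-go counts also pool Phase Ib subjects, for whom response is a secondary endpoint.

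If confirmation were really optional, the primary estimate and the input to the development decision would depend on who derived them. At a threshold, one response changes the reading.

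**Working it through.** **1. The plan's own figures.** With prior Beta(a, b) and x responses in n subjects, the posterior is Beta(a + x, b + n − x). SAP 2.2 gives Beta(0.45, 0.55) and a 40% target for IHC+, and Beta(0.2, 0.8) and a 30% target for IHC−. For 12 of 25, Beta(12.45, 13.55) gives P(ORR > 40%) = 0.788, as stated. The others also reproduce: 8/25 0.797, 18/40 0.737, 14/40 0.744, 6/15 0.757, 3/15 0.845, and 0/6 0.991 (stated as above 0.99).

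**2. What one response is worth at a boundary.**

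| Cohort | Count | Reading | Posterior probability |
|---|---|---|---|
| IHC+, n = 25 | 12 → 11 | Go → Evaluate | P(>40%) 0.788 → 0.655 |
| IHC+, n = 25 | 9 → 8 | Evaluate → No go | P(<40%) 0.661 → 0.797 |
| IHC+, n = 40 | 18 → 17 | Go → Evaluate | P(>40%) 0.737 → 0.624 |
| IHC+, n = 40 | 15 → 14 | Evaluate → No go | P(<40%) 0.629 → 0.744 |
| IHC−, n = 15 | 6 → 5 | Go → Evaluate | P(>30%) 0.757 → 0.560 |
| IHC−, n = 15 | 4 → 3 | Evaluate → No go | P(<30%) 0.662 → 0.845 |

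The primary estimate moves from 12/25 = 48% (95% interval 27.8 to 68.7) to 11/25 = 44% (24.4 to 65.1). Any integer threshold behaves this way; the table does not show that the count is ambiguous.

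**3. Is the count ambiguous?** The chain is: the endpoint is ORR per RECIST v1.1; the protocol's RECIST standard is its Appendix 2; that appendix requires confirmation when a non-randomised trial has response as its primary endpoint; Phase II is such a setting; and the scan that supplies confirmation is compulsory. To count unconfirmed responses, an analyst would have to set aside two explicit statements in Appendix 2. No sentence in either document tells anyone to do so.

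**4. Timing.** Scans fall at weeks 9 and 18. A response first seen at week 9 has its confirmatory scan at week 13, before the second scheduled scan. A response first seen at week 18 is confirmed at week 18 + 4 = 22. Only late-enrolled subjects in the second group can be pending, for about four weeks. The criteria say at least two assessments and do not bind, so waiting fits the text.

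**5. Missing or unevaluable scans.** With no imputation, a subject lacking the evidence for CR or PR is not a responder and stays in a denominator made up of treated subjects. Appendix 2 tabulates the unevaluable time point and describes PR, unevaluable, PR as reasonably taken to be confirmed in most trials. Those two conventions cover the cases likely to arise.

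**6. The duration rule.** Appendix 2 starts duration when CR or PR criteria are first met. A confirmed responder therefore always has a later scan and can never fall under the rule. It is idle for confirmed responders and does not affect ORR.

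**7. Pooling and pointers.** Appendix 2 speaks of trials, not phases, and Table 2 footnote k makes the confirmatory scan compulsory in Phase Ib too, so one definition can serve the pooled count. The SAP appendices carry protocol numbering throughout (Section 1.2, Appendix 6 and Appendix 8 are all protocol places). The Appendix 2 pointer is the same copying slip, and Section 3.5 in SAP 3.9 is evidently meant as 3.6.

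**The case for a change.** The strongest case for a change is that Appendix 2 hands one question to the analysis plan in terms: "The analysis plan for the trial must address how missing data/assessments will be addressed in determination of response and progression". The SAP does not answer it for response, and a primary endpoint should not have to be assembled from an appendix of another document. Unconfirmed responses do occur in the sponsor's evidence: the 11/63 benchmark from BLU-554-1101 includes one unconfirmed CR. If 40% of subjects show any response and 100%, 90%, 80% or 70% of these are confirmed (assumed shares), the chance of Go at 25 on a confirmed count is 0.268, 0.149, 0.070 or 0.026.

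The first part stands as a remark on drafting: the SAP would be clearer with the word and the convention written in. The rest carries less. The documents give no usable confirmation share: 1 of 11 has an exact 95% interval of 0.2% to 41%, and the protocol does not say whether that subject had a confirmed PR. The falling probabilities measure the distance between two definitions, only one of which the documents allow. For the benchmark, 11/63 = 17.5% against 10/63 = 15.9% is a difference of 1.6 points, in a figure that serves as background to the target and not as a comparator.

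**Conclusion.** The omission is real but small. SAP 3.6, protocol 10.4 and the go/no-go criteria do not repeat a requirement that protocol Appendix 2 already imposes and that the schedule already supports with a compulsory scan. The documents followed as written give a confirmed ORR. The undefined term, the handling of unevaluable or missing confirmatory scans, and the short wait for a pending scan are details that analysts settle sensibly in the derivation specification; the two wrong cross-references are clerical.

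One response at a boundary changes a reading, for example 0.788 to 0.655 at 12 against 11 of 25, but those readings are advisory, there is no hypothesis test, and no effect on the result is demonstrated. The conclusion assumes that the analyst applies protocol Appendix 2 as the RECIST standard for the trial, pooled Phase Ib subjects included. On that footing the plan needs no change.

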### Safety

As of the data cutoff, a total of 115 subjects were evaluable for the safety analysis evaluation. Most adverse events (AEs) observed in these subjects were Grade 1 or 2. The most common ( $\geq$ 20%) suspected to be related to study drug include diarrhea (N = 87, 76%), nausea (N = 48, 42%), ALT increased (N = 38, 33%), vomiting (N = 42, 37%), AST increased (N = 33, 29%), fatigue (N = 32, 28%) and decreased appetite (N = 22, 19%). Serious adverse events (SAEs) were reported in 49 (43%) subjects, and SAEs considered related to study drug occurred in 18 (16%) subjects, mainly including vomiting, anemia, hyponatremia, and pyrexia, etc.

At the time of the data cut-off, 10 of 115 subjects remained on treatment, including 9 subjects

CSTONE Confidential Page 50 of 139 who are FGF19 IHC+. Of the 105 subjects (91%) who discontinued treatment with BLU-554,78 subjects ended treatment due to disease progression, 18 due to AEs, 6 due to withdrawal of consent, and 3 due to Investigator decision. No deaths due to drug-related AEs have been reported.

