## 5.6.2. Follow-up of Subjects Who Discontinue Treatment

Subjects who discontinue the study drug must continue to be followed, and outcome and/ or survival follow-up data will be collected as required until death, loss to follow-up or end of study.

Subjects who stopped treatment before clearly documented disease progression will continue to undergo imaging examination and tumor evaluation every 9 weeks ( $\pm$ 7 days) within 1 year and every 12 weeks ( $\pm$ 7 days) after 1 year until presence of any of the followings: (1) disease progression, (2) initiation of new anti-cancer therapy, (3) withdrawal of informed consent, (4) loss to follow-up, (5) death, (6) termination of study, whichever occurs first.

Loss to follow-up is that the contact cannot be established with the subject, and there is insufficient information to determine the status of the subject at that time. Subjects who refuse survival follow-up should be defined as withdrawal of consent instead of loss to follow-up.

For loss to follow-up subjects, the site should contact the subject as much as possible to determine the reasons for loss to follow-up and try to reschedule the visit. The process of attempting to contact the subject should also be documented and the date contacting the subject and the contact information used will be documented in the study file.

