#### 7.2. EFFICACY ASSESSMENTS

Efficacy assessments will be performed by the investigator and BICR, respectively, according to RECIST v1.1.

Radiographic (CT or MRI) assessments will be performed within 28 days prior to the first dose (baseline assessment), every 9 weeks during the first year of the study and every 12 weeks thereafter, according to RECIST v1.1 (APPENDIX 2: THE LATEST REVISED RECIST GUIDANCE (VERSION 1.1))) until 1) disease progression, 2) initiation of new anti-cancer therapy, 3) withdrawal of informed consent, 4) loss of follow-up, 5) death, 6) termination of study, whichever occurs first. In addition to subjects who discontinue treatment due to disease progression as determined by radiographic assessment, additional subjects should continue to undergo radiographic assessments at the scheduled time. Baseline tumor assessment should include brain (phase II study only), chest, abdomen, pelvis and other sites suspected of tumor lesions, and subsequent evaluations should include all sites evaluated at baseline (phase II study: subjects who have no brain metastases confirmed by imaging at screening will not be required to undergo regular brain imaging at subsequent visits, which may be scheduled by the investigator as clinically indicated), and should be performed using the same imaging method used at baseline. If a subject has undergone a bone scan within three months of baseline assessment and was determined to be negative, the bone scan was not required for the baseline assessment. For subjects with bone metastases at screening, bone lesions should be followed up at subsequent visits. For subjects without bone metastases at baseline, follow-up with bone lesions is not required, unless the subject develops symptoms. The same detection technique as the baseline was used throughout the study. If an unscheduled tumor assessment occurs and the subject does not experience disease progression, subsequent tumor assessments should also be performed as scheduled.

All radiographic results in this study will be interpreted by the sites or radiologists. The subjects will be clinically managed (including continuation or discontinuation of study treatment) based on the investigator's assessment of tumor imaging and the investigator's clinical judgment during the study.

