#### Survival follow-up:

From the last dose of study drug, subjects will be contacted by telephone or face-to-face every 12 weeks, to collect subject survival status, subsequent anti-tumor therapy and study drug-related SAEs until the death, loss of follow-up, withdrawal from the study, or study termination, whichever occurs first.

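### PFS counts a death at any distance from the last scan, although scanning stops at new anti-tumour therapy, so subjects who switch without PD and then die get PFS times that are too long

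*SAP*

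**What the plan says.** **PFS.** SAP 3.6 states: "PFS is defined as the time from the date of first study dose to disease progression or death (whichever occurs first". The only censoring rule is "Subjects without event (no disease progression or death) will be censored at the date of" the last tumour assessment. Protocol 10.4 has the same definition and the same rule.

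**When scans stop.** Protocol 7.2 schedules imaging "every 9 weeks during the first year of the study and every 12 weeks thereafter" and continues it "until 1) disease progression, 2) initiation of new anti-cancer therapy, 3) withdrawal of informed consent", loss to follow-up, death or study termination. Footnote k of the schedules of activities agrees. For subjects off study drug, Protocol 5.6.2 says: "Subjects who stopped treatment before clearly documented disease progression will continue to undergo imaging examination and tumor evaluation every 9 weeks" (12-weekly after one year), "until presence of any of the followings: (1) disease progression, (2) initiation of new anti-cancer therapy", or one of the other stopping reasons.

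**What is still collected.** The survival follow-up in Protocol 7.5.4 contacts subjects every 12 weeks "to collect subject survival status, subsequent anti-tumor therapy and study drug-related SAEs until the death" or another end point. Footnote s of the schedules records start dates of subsequent therapy.

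**Other censoring text.** SAP 3.9 refers efficacy censoring to Section 3.5, which is the safety analysis and has no such rule. The missing-date appendix of the SAP deals only with incomplete dates.

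**DOR.** Both documents define the event as PD or death from any cause. Protocol 10.4 then censors only responders who are alive without progression. SAP 3.6 censors all responders without PD, which on a literal reading includes those who died.

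**The concern.** Counting every death regardless of later treatment is a coherent choice if progression stays observable after the switch. Here it does not. Once a new therapy starts, no scan can show PD, but a death many months later is still captured and scored at its own date. The death stands in for a progression that would normally have been seen earlier.

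Subjects on this path are also scored by whether they have died by cut-off, not by their disease course: a late event if dead, an early censoring if alive. The RECIST text in Protocol Appendix 2 says that, where response confirmation is required, the analysis plan must address missing assessments when progression is determined. This SAP does not.

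At stake are the PFS medians and landmark rates and, through the protocol wording, DOR. DOR is one of the endpoints to be weighed when the response count falls in the evaluate range.

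**Working it through.** The plan states no PFS median, event count or new-therapy rate, so there is no figure to reproduce. The check is a trace of the rule followed by an illustrative simulation.

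**1. Trace.** Take a subject with SD at the week 9 scan, new therapy at week 12 and no PD.
- Dies at week 60: PFS event at 60 weeks, which is 60 − 9 = 51 weeks after the last scan.
- Alive at cut-off: censored at week 9.

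**2. Who can be affected.** Only subjects whose scanning has ended without PD and who then die by cut-off. Stopping drug alone does not end scanning (Protocol 5.6.2). After consent withdrawal, survival is collected only if consent to disclosure remains (Protocol 5.6.3).

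**3. A proxy for the rate.** For BLU-554-1101, the Safety text of Protocol 2.4.1.1 says that 78 "subjects ended treatment due to disease progression, 18 due to AEs, 6 due to withdrawal of consent, and 3 due to Investigator decision". Stops without PD: 18 + 6 + 3 = 27, and 27/115 = 23.5%. This counts treatment stops, not new-therapy starts, so it is an upper proxy. Without the six consent withdrawals it is 21/115 = 18%.

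**4. Simulation inputs.**

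| Input | Value | Source |
|---|---|---|
| Scan interval | 9 weeks = 2.07 months | Protocol 7.2 |
| Median time to progression | 4.3 months, exponential | Assumption: the CS1001 phase Ia PFS median (Protocol 2.4.1.2; 29 subjects, mixed tumours) |
| Median OS | about 12 months | Assumption |
| New therapy as share *f* of exits | 5% to 23% | Assumption |
| Cut-off | 24 months | Assumption |

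Progression hazard: ln 2 / 4.3 = 0.161 per month. New-therapy hazard: 0.161 × *f*/(1 − *f*), first taken as independent of progression.

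Hand check of the continued-scanning curve: PD shows only at scans, so 12-month PFS is roughly the chance of no progression by the fifth scan, exp(−0.1612 × 10.35) = 18.9%. At 9 months, using the fourth scan, it is exp(−0.1612 × 8.28) = 26.3%. The simulation gives 18.6% and 26.2%; the small shortfall is deaths before the next scan.

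**5. Results, independent switching.**

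| *f* = 23% | As written | Scans continue | Censored at last scan before new therapy |
|---|---|---|---|
| 9-month PFS | 32.0% | 26.2% | 26.2% |
| 12-month PFS | 23.4% | 18.6% | 18.5% |

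The 12-month inflation is 23.4 − 18.6 = 4.8 points. The standard error at n = 40 is √(0.186 × 0.814/40) = 6.15 points, so the bias is 4.8/6.15 = 0.8 SE. At *f* = 5%, 10% and 15% the inflation is about 1, 2 and 3 points. The median moves little: 6.2 months as written against about 5.9-6.1.

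**6. Results, switching shortly before progression, 23%.** 12-month PFS is about 25-26% as written, about 25% with the censoring rule and 18-19% with continued scanning. Censoring then removes almost none of the bias.

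**7. Slower disease course.** Assumptions: median progression 26 weeks, median post-progression survival 40 weeks, 10-30% assigned to switch, mean follow-up 78-104 weeks, switching either independent or anticipating progression. Subjects who switch without PD and then die are 2.5-19% of all subjects. Their PFS is recorded 18-27 weeks late on average. PFS at 52 weeks rises by 0.2-8.8 points. The median goes from 27 weeks to between 27 and 36, because it jumps from scan to scan.

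**The case against.** **Most subjects who leave treatment are still scanned.** This stands. A reader might infer that everyone who stops without PD gets an inflated PFS time. Protocol 5.6.2 and footnote k rule that out: subjects who stop, for example for an adverse event, stay on the imaging schedule. Switchers who are alive at cut-off are not inflated either; they are censored early.

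**The rate is unknown.** This stands. A reader might take 23% as the expected switching rate. The documents do not support that, since it counts treatment stops in another study. The 4.3-month input comes from CS1001 alone in mixed tumours.

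**Censoring is no cure.** This stands in part. It restores the continued-scan curve only if switching is unrelated to progression. Starting a new cancer therapy may well anticipate progression, so a second sensitivity analysis is needed.

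**Any-death PFS is a legitimate treatment-policy estimand.** This does not rescue the plan, because that estimand needs scans after the switch and the protocol stops them.

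**The stakes are low.** Largely right. PFS and DOR are secondary, single-arm and descriptive.

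**Conclusion.** The mismatch is in the current text of both documents, and nothing elsewhere repairs it. Followed as written, the rule makes PFS too long for subjects whose scanning ends without PD, mainly through new therapy, and who then die by cut-off.

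The direction was upward in every scenario. The size is illustrative: about 1-3 points on 12-month PFS at 5-15% switching and about 5 points at 23%, within one standard error at n = 40. It rests on borrowed progression and survival medians and an assumed switching rate.

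DOR under Protocol 10.4 has the same problem. A reader might infer that SAP 3.6 counts deaths in DOR the same way; its definition does, but its censoring sentence does not, so the SAP's DOR rule is unresolved. A reader might also infer that the go/no-go thresholds are affected. They count responses, are stated to be non-binding and do not depend on PFS. This is a cheap improvement, not a threat to the primary endpoint.

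**What to change.** Add to SAP 3.6 and Protocol 10.4:

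*Subjects who start a new anti-tumour therapy without documented PD are censored for PFS and DOR at the last evaluable tumour assessment before that therapy. PD or death that follows two or more consecutive missed scheduled assessments is censored at the last evaluable assessment before the gap.*

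Add two sensitivity analyses:
- the current any-death rule;
- start of new anti-tumour therapy counted as an event, because censoring leaves the bias in place if switching anticipates progression.

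In the same edit, align the SAP 3.6 DOR censoring sentence with its definition, and correct the SAP 3.9 cross-reference from Section 3.5 to Section 3.6.

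Cost: wording and two derivation rules. Therapy start dates are already collected. The downsides are slightly fewer PFS events and possible informative censoring, which the second sensitivity analysis addresses.
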